# **Protocol Summary**

**Title**: Metagenomic Studies of MRSA Colonization - Nose, Throat, and Skin Cultures before and after use of Antibacterial Nasal Ointment and Antibacterial Soap for Showering in Adults who live in the Community and have Current *S. aureus* Colonization

**Population**: Approximately 250 male and female adults with *S. aureus* colonization at enrollment from a single geographic location in the US to achieve a final sample size of at least 40.

Site: Baltimore VA Medical Center

[figure not shown]
Study Duration: Approximately 18 months

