### 5.2 Inclusion Criteria

- Adults living independently in the Baltimore area
- Willing and able to provide anterior nares, throat, skin, and perirectal specimens over up to an 18 week time period.
- Willing and able to administer intranasal mupirocin and topical chlorhexidine over a five day period.
- Capable of understanding and complying with the entire study protocol.
- Provided signed and dated informed consent.
- *S. aureus* colonization on at least one of the enrollment cultures (after informed consent)

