### 7.2 Dosage, Preparation and Administration of Study Intervention

Participants will be self-treated with antimicrobial antiseptic skin cleanser (4% chlorhexidine) topically 3 times within 5 days before the Week 9 visit. Participants will also be self-treated with BACTROBAN NASAL ointment (mupirocin calcium ointment, 2%) intranasally in the 5 days before the Week 9 visit.

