### 7.5 Assessment of Participant Compliance with Study Intervention

At the Week 8 study visit, three doses of antimicrobial antiseptic skin cleanser (4% chlorhexidine) and ten doses of BACTROBAN NASAL ointment (mupirocin calcium ointment, 2%) will be dispensed to all participants. Instructions regarding dosing, missed doses and possible side effects will be provided. In addition, a Compliance log will be provided for the participant to document the date and time required study doses were taken. In addition, missed doses will be recorded on this log and the participant will be instructed to call the Investigator if two or more doses are missed. The Investigator may decide to provide the participant with an additional two doses.

At the Week 9 study visit, the log will be reviewed to determine compliance with study medication.

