- Counsel participant to refrain from using any antibacterial/antiseptic products for 48 hours before visits.
- Counsel participant to refrain from swimming in a chlorinated pool or using a hot tub in the 48 hours before visits.
- Counsel participant to refrain from bathing or showering in the 12 hours prior to the next study visit.

Week 8 – Will occur in the GCRC:

- Reconfirm participant's willingness to participate in the study.
- Confirm that participant has abstained for the last 48 hours from the following: using any antibacterial/antiseptic products, swimming in a chlorinated pool or using a hot tub.
- Record time and date of last bath or shower.
- Measure oral temperature to screen out participants with febrile infectious disease.
- Collect a focused medical history.
- Review concomitant medications
- Complete a brief physical assessment of their anterior nares, posterior pharynx and skin sites.
- Obtain specimens from the anterior nares, posterior pharynx, skin over subclavian vein, skin over femoral vein and perirectal skin.

For participants who meet eligibility criteria to continue in the study:

- Provide a 16oz of antimicrobial antiseptic skin cleanser (4% chlorhexidine) to participant. Educate participant on how to use the skin cleanser in the shower on all of their skin from the neck down.
- Provide ten doses of mupirocin ointment to participants. Educate participant on how to self-apply the ointment intranasally.
- For each medication, provide instructions regarding application, dosing, missed doses and possible side effects.
- Provide a Compliance Log to participant to document the date and time required study doses are taken. Instruct participant to also record missed doses on the log, and to call the Investigator if two or more doses are missing. The Investigator may decide to provide the participant with an additional two doses.
- Counsel participant to refrain from using any antibacterial/antiseptic products for 48 hours before visits.
- Counsel participant to refrain from swimming in a chlorinated pool or using a hot tub in the 48 hours before visits.
- Counsel participant to refrain from bathing or showering in the 12 hours prior to the next study visit.

Week 9 – Will occur in the GCRC:

- Reconfirm participant's willingness to participate in the study.
- Confirm that participant has abstained for the last 48 hours from the following: using any antibacterial/antiseptic products, swimming in a chlorinated pool or using a hot tub.

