- Record time and date of last bath or shower.
- Measure oral temperature to screen out participants with febrile infectious disease.
- Collect a focused medical history.
- Review concomitant medications.
- Complete a brief physical assessment of their anterior nares, posterior pharynx and skin sites.
- Obtain specimens from the anterior nares, posterior pharynx, skin over subclavian vein, skin over femoral vein and perirectal skin.
- Review the Compliance Log to determine compliance with the 5-day course of mupirocin/chlorhexidine.
- Counsel participant to refrain from using any antibacterial/antiseptic products for 48 hours before visits.
- Counsel participant to refrain from swimming in a chlorinated pool or using a hot tub in the 48 hours before visits.
- Counsel participant to refrain from bathing or showering in the 12 hours prior to the next study visit.

Weeks 10, 11, 12, and 16-Will occur in the GCRC:

- Reconfirm participant's willingness to participate in the study.
- Confirm that participant has abstained for the last 48 hours from the following: using any antibacterial/antiseptic products, swimming in a chlorinated pool or using a hot tub.
- Record time and date of last bath or shower.
- Measure oral temperature to screen out participants with febrile infectious disease.
- Collect a focused medical history.
- Review concomitant medications
- Complete a brief physical assessment of their anterior nares, posterior pharynx and skin sites.
- Obtain specimens from the anterior nares, posterior pharynx, skin over subclavian vein, skin over femoral vein and perirectal skin.
- Counsel participant to refrain from using any antibacterial/antiseptic products for 48 hours before visits.
- Counsel participant to refrain from swimming in a chlorinated pool or using a hot tub in the 48 hours before visits.
- Counsel participant to refrain from bathing or showering in the 12 hours prior to the next study visit.

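### Sections 7.2 and 8.1 contradict each other on mupirocin in the 48 hours before the Week 9 visit, so the interval from last dose to the first post-treatment sample is not fixed

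*Protocol*

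**What the plan says.** Section 7.2 has participants use mupirocin "intranasally in the 5 days before the Week 9 visit" and the chlorhexidine cleanser "topically 3 times within 5 days before the Week 9 visit". Under Section 7.5, "ten doses of BACTROBAN NASAL ointment (mupirocin calcium ointment, 2%) will be dispensed to all participants" at Week 8, with three doses of the cleanser and a Compliance Log for the date and time of each dose. No section states how many mupirocin doses are taken per day. The five-day length appears twice more: in the inclusion criteria of Section 5.2 ("Willing and able to administer intranasal mupirocin and topical chlorhexidine over a five day period") and in the Week 9 list of Section 8.1 ("Review the Compliance Log to determine compliance with the 5-day course of mupirocin/chlorhexidine").

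The Week 8 list in Section 8.1 hands out both products and then counsels participants to avoid antibacterial and antiseptic products in the 48 hours before visits. The Week 9 list has staff verify this: "Confirm that participant has abstained for the last 48 hours from the following: using any antibacterial/antiseptic products". The same check appears at Weeks 4, 8, 10, 11, 12 and 16. No list exempts the study products, and they fall within the rule's own terms: the title in the Protocol Summary speaks of cultures "before and after use of Antibacterial Nasal Ointment and Antibacterial Soap for Showering", and Section 4.2 calls chlorhexidine an antiseptic.

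**The concern.** At Week 9 staff check two things: that the five-day course was taken, and that nothing antibacterial was used in the last 48 hours. For mupirocin timed as in Section 7.2, both cannot be true.

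The protocol does not say which rule gives way. A participant who stops early has taken less of the course. One who continues to the visit has a shorter gap before sampling. One who starts on the day of the Week 8 visit may do neither. Exposure and time since last dose can then differ between participants at the first post-treatment sample. That sample feeds the first within-person comparison before and after decolonization (Section 11.1, Aim 2), and it opens the follow-up for weeks to re-colonization (Section 11.2). Section 8.1 also says that specimens collected off schedule are not reported as deviations, so deviation reports would not show the spread.

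**Working it through.** This is calendar arithmetic. The plan's own figures are ten mupirocin doses and three chlorhexidine uses in five days.

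**Inputs**
- Mupirocin: 10 doses (Section 7.5), in the 5 days before Week 9 (Section 7.2).
- Chlorhexidine: 3 uses within the same 5 days (Section 7.2).
- Barred period: 48 hours = 2 days before the visit (Section 8.1).
- Nominal gap from Week 8 to Week 9: 7 days. Section 8.1 says exact timing is not required. Its spacing guidelines cover the three sets before treatment and the four after it, but give no minimum gap between the third and fourth sets.

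**Mupirocin, Section 7.2 taken literally**
- Days left outside the barred period: 5 − 2 = 3.
- Assumed even spacing: 10 / 5 = 2 doses a day.
- Doses that fit: 3 × 2 = 6 of 10. Doses in the barred period: 2 × 2 = 4 of 10, or 40%.
- The conflict does not depend on that assumption, although the 4 of 10 does. At any daily frequency, a course filling the five days before the visit includes the last two.

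**Chlorhexidine, at most one use a day (assumed)**
- Ways to place 3 uses in 5 days: 5! / (3! × 2!) = 10.
- Only one avoids the last two days: the fifth, fourth and third days before the visit. Both rules can be met, but only that way.

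**Course begun at Week 8 instead**
- Interval left before Week 9 = gap − days of delay in starting − 5.

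| Gap between visits | Start on day of Week 8 visit | Start one day later |
|---|---|---|
| 6 days | 1 day | 0 days |
| 7 days (nominal) | 2 days | 1 day |
| 8 days | 3 days | 2 days |

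- At the nominal gap, 5 + 2 = 7 days leaves no slack. A one-day delay or a visit one day early breaks the 48-hour rule.
- Section 7.5 lets the Investigator supply two more doses after missed doses. If these lengthen the course by a day (at the assumed 2 a day), the interval falls to 7 − 6 = 1 day.

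Within the nominal 7 days, the interval from last dose to the Week 9 sample can therefore run from about 0 to 2 days for a completed course, and no section fixes it.

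**The case against.** The best reply is that the 48-hour bullet is standing text repeated from Week 4 to Week 16 and aimed at non-study products. Staff also give dosing instructions at Week 8, and Section 8.1 refers to SOPs that are not shown. This is plausible and may be what was meant. But the wording covers every such product without exception, and it sits in the same Week 8 list that dispenses the study products. An SOP could settle practice, yet Sections 7.2 and 8.1 would still disagree.

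Several limits on the point stand:
- The strict conflict is for mupirocin only.
- The Week 8 start shows that a complete course and 48 clear hours can coexist. A reader might infer that every participant is either under-dosed or sampled under residual drug; that choice is not exhaustive.
- Week 8 counselling asks for no bath or shower in the 12 hours before the next visit, and the cleanser is used in the shower. Someone who follows it has at least 12 hours between last chlorhexidine use and sampling, and Week 9 records the time of the last bath or shower. This does nothing for mupirocin.
- A reader might infer that residual drug produces false-negative cultures. The protocol gives no information on drug persistence or carry-over, so it does not support this.
- A reader might treat Week 9 as the decisive sample. It is the first of four weekly sets, followed by sets at about Week 16 and Month 12, and no section ties successful decolonization to it.

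**Conclusion.** The contradiction is real and confined to mupirocin around one visit. A full course timed as in Section 7.2 cannot satisfy the Week 9 abstention check, and about 4 of 10 doses fall in the barred 48 hours if dosing is even at an inferred 2 a day. The statistical consequence is an unfixed interval from last dose to the first post-treatment sample, possibly with differing exposure. It bears on the first comparison with baseline and on the start of re-colonization follow-up. The later sets fall after the course and are not touched by the timing conflict itself, although any shortened course would carry into them.

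The documents do not show that every participant would fail the check: that requires everyone to follow 7.2 literally and the rule to include study products. Nor do they state any consequence of failing. How far participants would actually differ cannot be known from the protocol.

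**What to change.** Reconcile Sections 7.2 and 7.5 with the Week 8 and Week 9 lists in Section 8.1. State whether the 48-hour rule covers the study products, and how the course is timed relative to the Week 9 sample. The clinical team decides both; this review does not favour either rule.

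On the data side, carry the date and time of the last dose of each product from the Compliance Log into the analysis dataset. Account for time since last dose when analysing Week 9, and show Week 10 results beside Week 9. If a separate analysis plan exists, the analysis wording belongs there.

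The cost is a clarification in the protocol and participant instructions, entry of an item already logged, and one added display. Week 10 specimens are already scheduled, and the data steps also help for participants already treated.

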#### Month 12 (+/- 3 months) Follow-up visit- Will occur in the GCRC

Clinical procedures are completed by GCRC staff. However, in extreme circumstances it is possible for this study visit to be completed at the participant's home, in which case the follow-up visit procedures are completed by a trained research staff member.

- Participants previously enrolled prior to 12 month follow-up visit being added, will need to be re-consented at the 12 month follow-up visit prior to any data/specimen collection.
- Participants who were consented for the 12 month follow-up visit will have the consent form reviewed with them prior to any data/specimen collection.
- 1) Obtain nose culture see Appendix 2 "Method for Obtaining Nose Culture".
- 2) Obtain throat culture see Appendix 3 "Method for Obtaining Throat Culture".
- 3) Obtain skin cultures see Appendix 4 "Method for Obtaining Skin Cultures".
- 4) Interview participant and complete the follow up visit form.

The visit time points represent ideal visit times, but this exact timing is not required. We will be using the following guidelines:

- 1) All follow-up visits through visit 8 must occur no more than 18 weeks after enrollment.
- 2) Participants should have 3 sets of specimens collected in the 2 months prior to administration of chlorhexidine/mupirocin. These initial 3 sets of specimens can occur no closer than 2 weeks apart.
- Participants should have 4 sets of specimens collected in the 4 weeks after chlorhexidine/mupirocin administration. These 4 sets of specimens can occur no closer than 5 days apart.
- 4) Participants should have an 8thset of specimens collected after the 4 weekly sets of specimens. This 8th set of specimens can occur no closer than 2 weeks after the last weekly specimens (which should have been collected at approximately week 12).
- 5) The 12 month follow-up visit should occur between the 9th and the 15th month after the partciapants original date of enrollment in the study.

Specimens not collected at the designated time or missed altogether will not be reported as deviations. Missed visits will not be reported as deviations.

See SOPS for detailed procedures of visit conduct, specimen collection, and case report forms.

### 8.2 Laboratory Evaluations

During each study visit a specimen is obtained by trained research personnel from each of the following sites: anterior nares, posterior pharynx, skin over the femoral vein, skin over the subclavian vein, and perirectal skin. These specimens are tested for MRSA, MSSA and gramnegative bacilli in the Research Microbiology Laboratory and are also analyzed for the presence of all bacteria using metagenomics techniques.

In addition, a blood sample taken at the enrollment visit will be initially processed in the GCRC and transported to the Research Microbiology Lab for storage until immunologic and genotypic tests are performed.

# 9 Unanticipated Problems and Serious Adverse Events

The methods of specimen collection in this microbiome sampling study pose only minimal risk to the study participants. As defined in 45 US Code of Federal Regulations (CFR) 6.102 (i), "Minimal risk means that the probability and magnitude of harm or discomfort anticipated in the research are not greater in and of themselves than those ordinarily encountered in daily life or during the performance of routine physical or psychological examinations or tests." The minimal

physical risks associated with the sampling procedures are described in Section 1.3 and in the informed consent document.

The nature of the information collected from participants may involve risk to their privacy. These risks are described in Section 2.3 and in the informed consent document.

The results of research cannot be foreseen, so it is possible that unanticipated problems may arise in the study. In addition to unexpected adverse events, there are other types of incidents, experiences, and outcomes that occur during the conduct of human subjects research that represent unanticipated problems but are not considered adverse events. For example, some unanticipated problems involve social or economic harm instead of the physical or psychological harm associated with adverse events. The investigator or designee is responsible for the detection and documentation of unanticipated problems and Serious Adverse Events (SAE) in participants participating in the study. Unanticipated problems and SAEs should be reported to the IRB and the VAMHCS PO and ISO per VA handbook 6500 and as outlined in the Manual of Procedures.

We will use the definition of Unanticipated Problems as specified in the VHA Handbook 1058.01. We will follow the reporting requirements specified in the VHA Handbook 1058.01. We will collect all of the information required to follow those reporting requirements.

### **10 Quality Control and Quality Assurance**

The PI and affiliated institution are responsible for conducting the study in compliance with the IRB-approved protocol, all applicable federal and state regulations, VHA Handbook 1200.05 Requirements for the Protection of Human Subjects in Research and the International Conference on Harmonization, E6 Good Clinical Practice by adhering to the requirements for collecting, documenting and reporting complete and accurate data. A separate Data Quality Assurance (QA) Plan will be developed for this protocol to describe the frequency of review of study related data and the roles and responsibilities for activities related to Quality Control (QC).

### **11 Statistical Plan**

#### 11.1 Analysis Plan for Microbial Community Profiling

In this project, we will utilize model-based statistical methods to study the dynamics and composition of the microbial communities present in the anterior nares, posterior pharynx and three skin sites in two populations (Protocol HP-51033 Nursing home dwelling MRSA Colonized Adults and this protocol) with and without current exposure to the healthcare environment, and before and after decolonization using treatment with topical chlorhexidine and intranasal mupirocin. These analyses will be performed in association with the various metadata collected and will be critical to be able to answer the various questions associated with our project, which include:

Aim 1:

Over time within individuals and at the nose and throat, and skin sites- what are the microbial communities present, their relative/absolute abundance? Are there differences between individuals at the nose and throat by living environment (community-dwelling vs. nursing home dwelling)? Aim 2:

What are the changes, within individuals, in the microbiome associated with decolonization over time at the nose, throat, and skin sites in term or composition and relative/absolute abundance?

What are the changes in the microbiome of each individual from the baseline to after decolonization at the nose, throat, and skin sites, in relation to decolonization and living environment (community-dwelling vs. nursing home dwelling)?

The assignment of 16S sequencing reads to OTUs will be performed using OTUPicker (23, 24), the Ribosomal Database Project Bayesian classifier (25) and Hidden Markov Chain modelsbased algorithms developed at UMD-IGS by Drs. [name] and [name] to classify a subgroup of OTUs to the species level (for details about the speciation analysis, see (26)). OTU classification data for each sample will then be utilized for model-based comparative analyses of community structure. Model-based approaches directly use the observed raw data, and minimize the loss of information by eliminating the data reduction steps associated with distance-based methods (used in OTU classification tools such as DOTUR (24), UNIFRAC (25) and SONS (23)). The Bayesian and likelihood statistical frameworks used in these approaches provide a probabilistic measure of confidence in the results and facilitate comparisons between the different models and methods through the use of model-selection strategies such as Bayes factors, Akaike's information criterion, Bayesian information criterion and decision theory, and hypothesis-testing approaches. Moreover, model-based approaches allow for incorporation of metadata along with data used to infer the group membership of OTUs that comprise the microbial communities under study. This information is then used to cluster these communities. Model-based approaches also provide a classification tool to assign newly sampled individuals to pre-existing groups that result from clustering approaches that take both metadata and microbial community composition into account.

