### 5 Selection and Withdrawal of Participants

### 5.1 Recruitment of Study population

All study participants will be adults that live in Baltimore or the surrounding area. Community dwelling participants will be recruited from the Managed Care Clinics of the Baltimore VA Medical Center (via an IRB approved flier), by conducting a screening of the VA medical records for patients with cultures positive for S. aureus in the last three years in the VA Maryland HCS (via an IRB approved letter mailing), and approved VA research registries (via an IRB approved letter). In addition, we will recruit from students and employees of the University of Maryland Baltimore and the VA Maryland HCS (via an IRB approved flier).

When contacted about participation, the study coordinator will review the information from the study flier or letter with the potential participant and answer questions. If the potential subject is interested in participating, the study coordinator will review the eligibility criteria prior to scheduling the Enrollment Visit in the General Clinical Research Center (GCRC) in order to screen out ineligible participants by history. Identifying information will only be collected on those potential participants who are scheduled for the screening/enrollment visit.

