# 8 Study Procedures/Evaluations

#### 8.1 Clinical Evaluations

Day 0 (enrollment visit) – Will occur in the GCRC:

- Screen participant regarding inclusion and exclusion criteria.
- Obtain informed consent.
- Obtain demographic information and a brief medical history by interview. The brief medical history includes current and recent medications and past medical and surgical history.
- Collect vital signs and basic anthropometric measurements in order to determine eligibility. Participants deemed eligible for the study will be enrolled at this visit.
- Measure oral temperature to screen out participants with febrile infectious disease.
- Complete a brief physical assessment of the culture sites.
- Obtain a 40 mL blood sample and specimens from the following sites: anterior nares, posterior pharynx, skin over the femoral vein, skin over the subclavian vein, and perirectal skin (see SOP for Methods).
- Counsel participant to refrain from using any antibacterial/antiseptic products for 48 hours before visits.
- Counsel participant to refrain from swimming in a chlorinated pool or using a hot tub in the 48 hours before visits.
- Counsel participant to refrain from bathing or showering in the 12 hours prior to the study visit.
- Inform participant that if specimens are negative for *S. aureus*, he/she will be withdrawn from the study at week 4.

For participants who do NOT meet eligibility criteria to continue in the study: (if MRSA and MSSA negative on all enrollment cultures)

- 1) Inform participant via phone that all enrollment specimens were MRSA and MSSA negative and withdraw him/her from the study.
- 2) Complete Participant Deactivation Form

Week 4 – Will occur in the GCRC:

- Review results of cultures from Day 0 to determine eligibility
- Reconfirm participant's willingness to participate in the study.
- Confirm that participant has abstained for the last 48 hours from the following: using any antibacterial/antiseptic products, swimming in a chlorinated pool or using a hot tub.
- Record time and date of last bath or shower.
- Measure oral temperature to screen out participants with febrile infectious disease.
- Collect a focused medical history.
- Review concomitant medications

- Complete a brief physical assessment of their anterior nares, posterior pharynx and skin sites.
- Obtain specimens from the anterior nares, posterior pharynx, skin over subclavian vein, skin over femoral vein and perirectal skin.

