### 11.2 Analysis Plan for Microbiologic Data

The goals of the microbiological analysis are two-fold. The first goal is descriptive to document the effectiveness of the regimen in reducing colonization with MRSA, MSSA and pathogenic Gram-negative bacilli at the body sites sampled. The second goal will compare the effectiveness of the regimen in the two different populations. We will assess whether there are differences in acquisition of GNB and antibiotic resistant GNB between community-dwelling and nursing home-dwelling adults. We will compare weeks to MRSA or MSSA re-colonization in each body site by living environment using survival curves and the Wilcoxon log rank test. We will compare whether there are differences in the acquisition (among those negative at baseline) of specific GNB and resistant GNB between community-dwelling and nursing MRSA or MSSA-colonized adults using chi-square tests or Fisher's exact test as appropriate.

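### Section 11.2 compares nursing-home and community adults with unadjusted tests only, although, as the protocol describes the two groups, MRSA/MSSA carriage type is tied to living environment

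*Protocol*

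**What the plan says.** **The comparator.** Protocol section 11.1 describes the analysis as covering "two populations (Protocol HP-51033 Nursing home dwelling MRSA Colonized Adults and this protocol) with and without current exposure to the healthcare environment". The aims that follow define the contrast as community-dwelling against nursing-home-dwelling.

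**Entry to this study.** Section 5.2 requires "S. aureus* colonization on at least one of the enrollment cultures". Section 8.1 withdraws a participant after enrollment cultures only "if MRSA and MSSA negative on all enrollment cultures", and section 5.4 agrees. A carrier of MSSA alone therefore stays in.

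**Recruitment.** Section 5.1: "Community dwelling participants will be recruited from the Managed Care Clinics of the Baltimore VA Medical Center". Other sources are VA patients with a positive S. aureus culture "in the last three years in the VA Maryland HCS (via an IRB approved letter mailing"), VA research registries, and a further stream: "we will recruit from students and employees of the University of Maryland Baltimore and the VA Maryland HCS".

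**The tests.** Section 11.2 makes comparing the regimen's effectiveness in the two populations its second goal. Weeks to MRSA or MSSA re-colonization are compared by living environment with survival curves and a log-rank-type test. Acquisition of GNB and resistant GNB, among those negative at baseline, is compared "using chi-square tests or Fisher's exact test as appropriate". No covariate, stratum or restriction to MRSA carriers is named. In this last comparison the nursing-home adults are described as colonized with MRSA or MSSA.

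**The concern.** The comparison is across two protocols and is not randomized. If one group was selected for MRSA and the other for any S. aureus, a difference in re-colonization or GNB acquisition may reflect the carried organism, where people live, or both. An unadjusted test cannot separate these. The problem is sharpest for re-colonization, because MRSA or MSSA status is part of that outcome.

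The argument in section 11.3 that participants act as their own controls protects the before-and-after contrast. It does not protect this one.

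The healthcare-exposure wording in 11.1 adds a smaller difficulty. It suggests that the community group has no current healthcare contact, but the recruitment sources include clinic patients and health-system employees.

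**Working it through.** **1. The group definitions side by side**

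| Point | Nursing-home protocol | This protocol |
|---|---|---|
| Carriage, by 11.1 and by 5.2, 5.4 and 8.1 | MRSA | MRSA or MSSA |
| Carriage as worded in 11.2 | MRSA or MSSA | MRSA or MSSA |
| Adjustment in 11.2 | none named | none named |

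If 11.1 is right, carriage type is unbalanced by design. If 11.2 is right, the balance is unknown, since the two MRSA shares could still differ. The nursing-home protocol is not at hand, so the documents cannot settle which holds. On either reading the tests in 11.2 take no account of carriage type.

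**2. The plan's own figure.** Section 11.3 gives 250 enrolled, about one in five colonized and 10 lost: 250 × 0.20 − 10 = 40, which matches the stated final sample. (Section 4.2 gives a goal of 50 completers; I use 40.) The protocol gives no outcome risk, MRSA share or nursing-home sample size.

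**3. How a spurious difference would arise (assumed inputs only).** Let p_M and p_S be the outcome risks in MRSA and MSSA carriers, and m the MRSA share in the community group. Take the nursing-home group as all MRSA, with no effect of living environment.

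- Community risk: p_C = m·p_M + (1 − m)·p_S
- Crude difference: d = p_M − p_C = (1 − m)(p_M − p_S)

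With p_S = 0.20, 40 per group and a two-sided 0.05 two-proportion test (normal approximation), the rejection probability is Φ((d − 1.96·SE0)/SE1) + Φ((−d − 1.96·SE0)/SE1). SE0 is the pooled and SE1 the unpooled standard error.

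| m | p_M | d | Rejection probability |
|---|---|---|---|
| 0.5 | 0.3 | 0.5 × 0.1 = 0.05 | 0.08 |
| 0.5 | 0.5 | 0.5 × 0.3 = 0.15 | 0.27 |
| 0.3 | 0.4 | 0.7 × 0.2 = 0.14 | 0.26 |
| 0.1 | 0.3 | 0.9 × 0.1 = 0.09 | 0.15 |
| 0.1 | 0.5 | 0.9 × 0.3 = 0.27 | 0.72 |

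For the third row, p_C = 0.3 × 0.4 + 0.7 × 0.2 = 0.26, the pooled risk is 0.33, SE0 = 0.105 and SE1 = 0.104, which gives 0.26.

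If p_M = p_S, then d = 0 and there is no bias. If MRSA carriers have the lower risk, the sign reverses. The GNB comparison uses only those negative at baseline, so fewer than 40 may count; that lowers the rejection probability but leaves d unchanged. The log-rank comparison was not modelled.

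**4. Cost of restricting to MRSA carriers.** The 95% half-width for a difference at a common risk of 0.30, with 40 in the nursing-home group, is 1.96 × √(0.21 × (1/40 + 1/n_C)).

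| Community participants, n_C | Half-width |
|---|---|
| 40 (all) | 0.20 |
| 20 (m = 0.5) | 0.25 |
| 12 (m = 0.3) | 0.30 |
| 4 (m = 0.1) | 0.47 |

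At 4 the approximation is rough, but the message is clear.

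**The case against.** A reader might infer more than the protocol supports.

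- **That only unadjusted tests are planned throughout.** This is not so. Sections 11.1 and its continuation plan model-based microbiome analyses done in association with metadata. The point applies to 11.2. Covariate lists may also sit in a statistical analysis plan that is not at hand. That defence is weaker for 11.2, which names its tests.
- **That the nursing-home group is certainly MRSA-only.** This rests on how 11.1 names the other protocol, and 11.2 points the other way. The supportable statement is that the two must be reconciled.
- **That the community group is healthcare-exposed apart from a hospitalization exclusion.** Section 5.3 also excludes recent systemic and nasal antimicrobials, indwelling devices, recent immunosuppression and planned surgery or hospitalization. The protocol does not say whether students or employees have patient contact. The aims and 11.2 use living environment as the analysed contrast, and an independently living employee or clinic patient is correctly classed as community-dwelling. The label is a wording point.
- **That age differs by design.** This is plausible from the recruitment sources, but no ages are given for either group.
- **That differences will be attributed causally to living environment.** Section 11.2 says only that differences will be assessed, and neither the endpoint statement in 4.1 nor the sample-size rationale rests on this contrast.

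These objections narrow the point. They do not remove it: 11.2 makes the cross-population comparison one of its two goals and fixes tests that ignore carriage type.

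**Conclusion.** The point holds for section 11.2. As the protocol describes the groups, MRSA/MSSA carriage is confounded with living environment, and the planned comparisons of re-colonization and GNB acquisition do nothing about it. Sections 11.1 and 11.2 also disagree on the nursing-home carriage criterion.

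The size and direction of any bias cannot be derived from the protocol. The 5 to 27 point differences and the 8% to 72% rejection rates show only the mechanism. They rest on assumed risks, MRSA shares and group sizes and should not be cited as estimates.

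A reader might also conclude that the MRSA-only comparison should become primary, or that age-adjusted regression should replace the planned tests. The documents do not support going that far. With 40 participants here, an unknown MRSA share and possibly little overlap in age, either choice trades confounding for imprecision or extrapolation.

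**What to change.** 1. Reconcile 11.1 and 11.2 on whether the nursing-home protocol enrolled MRSA carriers only or MRSA or MSSA carriers.
2. Keep the tests in 11.2. For each living-environment comparison add an analysis restricted to participants MRSA-positive at baseline in both protocols. If the nursing-home group includes MSSA carriers, stratify by baseline MRSA/MSSA status instead.
3. Report age by group, and describe the cross-protocol contrast as exploratory and non-causal.
4. In 11.1 replace the healthcare-exposure description with nursing-home versus community-dwelling.

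The cost is a few sentences. No new specimens are needed here, because section 8.2 already tests every visit's specimens for MRSA and MSSA; I assume that the nursing-home protocol recorded baseline status too. The drawback is precision: the restricted estimate may rest on few community participants, so it should be shown with its confidence interval beside the unrestricted result.
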